SleepFlex™ Treatment of Obstructive Sleep Apnea NCT04726514

June 15, 2023

Study Protocol (Summary)

Study participants with mild to moderate obstructive sleep apnea (OSA) underwent 12 weeks of active treatment with the SleepFlex™ program of head and neck exercises.

Statistical analysis includes paired t-tests to evaluate primary and exploratory outcomes in participants who completed the study.

Results Summary

Enrolled participants: 10

Participants with data for analysis: 7

Outcomes are presented as baseline vs. 12-week measures

Total AHI: 15.5±5.1 vs. 12.2±5.5 events/hour (p=0.11)

Supine AHI: 21.0±10.8 vs. 15.3±6.0 events/hour (p=0.048)

Non-supine AHI: 7.3±7.4 vs. 6.8±6.7 events/hour (p=0.064)

Maximal inspiratory pressure: 93±35 vs. 114±34 kPa (p=0.02)

Maximal expiratory pressure: 108±33 vs. 137±14 kPa (p=0.04)

Anterior tongue strength: 53±13 vs. 56±10 kPa (p=0.20)

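### Does showing baseline and week-12 values with a p-value, rather than the paired change and its confidence interval, call for a change to the plan?

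*Combined protocol and SAP*

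**What the plan says.** The Study Protocol (Summary) names one method: "Statistical analysis includes paired t-tests to evaluate primary and exploratory outcomes in participants who completed the study". The Results Summary gives "Enrolled participants: 10" and "Participants with data for analysis: 7", and then states that "Outcomes are presented as baseline vs. 12-week measures".

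Six rows follow in one format. The total AHI row, for instance, reads "Total AHI: 15.5±5.1 vs. 12.2±5.5 events/hour (p=0.11"), and the supine row "Supine AHI: 21.0±10.8 vs. 15.3±6.0 events/hour (p=0.048").

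The ± is not defined, and neither the significance level nor the sidedness of the tests is stated. The number of pairs is given once, not by outcome. No row carries a mean change, an SD or standard error of the change, or an interval. The document does not offer the ± terms as the precision of the change, and it draws no conclusion from any of the p-values.

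**The concern.** The analysis and its presentation concern different quantities. A paired t-test depends on the SD of each person's change. The printed ± values describe spread between people at each visit, and without the within-person correlation they cannot be turned into the SD of the change. Someone who treats the visits as independent will usually think the change less precise than it is.

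With seven people this could matter. A p-value of 0.11 for total AHI may be taken as no effect and 0.048 for supine AHI as a clear one, when the intervals behind them would show how little is settled in either case. A column for the change would cost almost nothing, because the paired test already produces it.

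**Working it through.** **Inputs (Results Summary).** Pairs n = 7, so 6 degrees of freedom. The means, ± values (s1, s2) and p-values are as printed.

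**Assumptions.** ± is an SD, p is two-sided, and there are 7 pairs in every row. Reading ± as a standard error would make the supine AHI, non-supine AHI and maximal expiratory pressure (MEP) rows impossible, so SD is the supported reading. MIP is maximal inspiratory pressure.

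**Step 1: do the printed p-values fit the printed values?** A paired p cannot be recomputed directly, because the SD of the change is absent. That SD must, however, lie between |s1 - s2| and s1 + s2, which bounds p.

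| Outcome | SD of change, limits | p, limits | Printed p |
|---|---|---|---|
| Total AHI | 0.4 to 10.6 | <0.001 to 0.44 | 0.11 |
| Supine AHI | 4.8 to 16.8 | 0.020 to 0.40 | 0.048 |
| Non-supine AHI | 0.7 to 14.1 | 0.108 to 0.93 | 0.064 |
| MIP | 1 to 69 | <0.001 to 0.45 | 0.02 |
| MEP | 19 to 47 | 0.007 to 0.15 | 0.04 |
| Tongue strength | 3 to 23 | 0.038 to 0.74 | 0.20 |

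Five rows fit and non-supine AHI does not. Unpaired tests would give 0.27, 0.25, 0.90, 0.28, 0.054 and 0.64 in the same order. None matches, so the printed p-values were not obtained by treating the visits as independent.

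**Step 2: recover the change and its interval from p.**
- t is the two-sided t quantile for the printed p on 6 df.
- SE = |difference| / t.
- 95% CI = difference ± 2.447 × SE.

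For total AHI: 12.2 - 15.5 = -3.3; t = 1.874; SE = 3.3/1.874 = 1.76; half-width 2.447 × 1.76 = 4.31; CI -7.6 to 1.0.

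**Step 3: compare with a reader who assumes independence.** That reader's standard error is sqrt((s1² + s2²)/7). For total AHI it is sqrt((5.1² + 5.5²)/7) = 2.84, and 2.84/1.76 = 1.61.

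| Outcome | Change | Paired SE | 95% CI | Independence SE | Ratio |
|---|---|---|---|---|---|
| Total AHI | -3.3 | 1.76 | -7.6 to 1.0 | 2.84 | 1.61 |
| Supine AHI | -5.7 | 2.30 | -11.33 to -0.07 | 4.67 | 2.03 |
| MIP | +21 | 6.68 | 4.65 to 37.35 | 18.4 | 2.76 |
| MEP | +29 | 11.1 | 1.8 to 56.2 | 13.5 | 1.22 |
| Tongue strength | +3 | 2.08 | -2.1 to 8.1 | 6.20 | 2.98 |

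**Step 4: the row left out.** For "Non-supine AHI: 7.3±7.4 vs. 6.8±6.7 events/hour (p=0.064") the same steps give SE 0.221, SD of change 0.221 × sqrt(7) = 0.58 and a ratio of about 17. The implied correlation is 1.002, which cannot occur. At the edge of rounding (difference 0.6, SDs 7.35 and 6.75) p can fall to about 0.038. The printed p is therefore attainable, but only with near-perfect correlation.

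**Step 5: stability.** Rounding alone moves the tongue-strength ratio between 2.2 and 4.5. Its interval ranges from about (-1.4, 5.4) to (-2.8, 10.8) as the change runs from 2 to 4 at p = 0.20. Comparing a single printed SD with the SD of the change, for the five coherent outcomes, gives ratios from 0.48 (MEP, week 12) to 2.36 (tongue strength, baseline). Even the direction of a naive reader's error depends on how the figures are misused.

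**The case for a change.** The best case for a change is that, with seven pairs, the interval carries the message and p alone can mislead in both directions. For total AHI the interval runs from a fall of 7.6 events/hour, which is 7.6/15.5 = 49% of baseline, to a rise of 1.0. For supine AHI it stops 0.07 short of zero. Readers should not have to invert a rounded p-value to learn this. In the non-supine row the inversion gives no coherent answer as printed, and a column for the change might have prompted someone to check it.

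Much of this stands as reporting advice. The paired change, its SD and interval, the pairs per outcome and a definition of ± would all make the listing more useful.

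It does not show that precision has been misstated. The document states no precision for the change and shows no error bars. The factor of 1.2 to 3.0 belongs to a hypothetical reader who ignores the statement that the tests are paired. The supine interval comes close to zero but excludes it, as it must when p is below 0.05. The readings of no effect or of benefit would be the reader's own. The non-supine inconsistency is a separate matter, to be checked against the source data whatever the table format.

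**Conclusion.** The observation is accurate but no change to the plan follows. A paired t-test suits two measurements on the same people, and printing the change would alter neither the test nor any p-value. If the same participants are seen at both visits, the mean change is the difference of the printed means. An approximate interval then follows from p for five of the six outcomes: total AHI -3.3 (-7.6 to 1.0), supine AHI -5.7 (-11.3 to -0.1), and the three strength measures as tabulated above. No stated conclusion or design decision depends on the missing column.

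This is a gap in reporting detail that an analyst with the data would fill as a matter of course. The intervals rest on ± being an SD, two-sided p-values and 7 pairs for every outcome, and they are approximate because the inputs are rounded. They describe only the 7 analysed of the 10 enrolled.

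### The non-supine AHI p-value (0.064) cannot credibly be reproduced from its own means and SDs with the stated paired t-test in 7 participants

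*Combined protocol and SAP*

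**What the plan says.** The Study Protocol (Summary) names one method: "Statistical analysis includes paired t-tests to evaluate primary and exploratory outcomes in participants who completed the study". The Results Summary gives "Enrolled participants: 10" and "Participants with data for analysis: 7", and sets out each outcome as a baseline value followed by a 12-week value.

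The row in question is "Non-supine AHI: 7.3±7.4 vs. 6.8±6.7 events/hour (p=0.064"). Its neighbours are "Total AHI: 15.5±5.1 vs. 12.2±5.5 events/hour (p=0.11") and "Supine AHI: 21.0±10.8 vs. 15.3±6.0 events/hour (p=0.048").

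The document gives no SD of the change, confidence interval, row-specific n, sidedness or alpha. It does not say which outcomes are primary, and it does not label the ± values.

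**The concern.** The non-supine mean falls by only 0.5 events/hour, against SDs of about 7, yet its p-value is smaller than the one for the 3.3 events/hour fall in total AHI (0.064 against 0.11). That ordering is not an error in itself, because a paired test depends on the SD of the within-person differences and not on the SDs at each visit. It does raise a question that can be checked: could the differences be consistent enough to give 0.064?

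At stake is how the non-supine result is read. Beside a supine p of 0.048, a value of 0.064 suggests an effect in both positions that narrowly missed significance in one of them. If the p-value is the wrong figure, there may be almost no evidence of change outside the supine position. A reader cannot settle this, because the row gives neither an interval nor an SD of the change.

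**Working it through.** **Inputs (Results Summary).** Baseline 7.3 (s₁ = 7.4); week 12 6.8 (s₂ = 6.7); p = 0.064; n = 7, so 6 df. Assumptions: ± means SD, and the test is two-sided on the raw scale. The correlation r between visits is not given, so it is solved for.

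**Formulas.** t = d√n / SD_diff, where SD_diff² = s₁² + s₂² − 2r·s₁·s₂. Since r cannot exceed 1, SD_diff cannot be below |s₁ − s₂|.

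**1. Attempt to reproduce the printed p.**
- p = 0.064 on 6 df needs t = 2.266.
- SD_diff = 0.5 × √7 / 2.266 = 0.584.
- Smallest SD_diff allowed: 7.4 − 6.7 = 0.700.
- Implied r = (7.4² + 6.7² − 0.584²) / (2 × 7.4 × 6.7) = 1.0015, which is impossible.
- At r = 1, t = 0.5 × √7 / 0.7 = 1.89 and p = 0.108. This is the floor for the figures as printed.

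**2. Allow for rounding.** The most favourable limits are a change of 0.6 (7.35 − 6.75), SDs of 7.35 and 6.75, and p = 0.0645. Then t = 2.2605, SD_diff = 0.6 × √7 / 2.2605 = 0.702 and r = 0.9987. When the means and SDs are drawn uniformly within their rounding limits, about 3% of combinations allow a p that rounds to 0.064 at any r up to 1.

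**3. Two-sided p at given correlations, n = 7.**

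| r | As printed | Most favourable rounding of means and SDs |
|---|---|---|
| 1 | 0.108 | 0.038 |
| 0.99 | 0.32 | 0.22 |
| 0.95 | 0.59 | 0.52 |
| 0.90 | 0.70 | 0.64 |

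Conversely, with the printed SDs, p = 0.064 needs a mean change of 2.0 events/hour at r = 0.95 (SD_diff 2.33) or 2.8 at r = 0.90 (SD_diff 3.23).

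**4. Other readings of the row.**
- One-sided, n = 7: r = 0.9993 as printed, 0.9954 at the rounding limits.
- All 10 enrolled, two-sided: the same two values.
- n = 8 or 9, as printed: implied r still above 1 (1.0008 and 1.00002).
- n = 6, same summaries: the floor rises to 0.141.
- ± read as standard error: t is at most 0.5/0.7, so p is at least 0.50.
- Unpaired t-test, 12 df: p = 0.90.
- Exact signed-rank test, 7 untied pairs: 0.047 and 0.078 are adjacent attainable values, so 0.064 is not attainable.

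**5. Same inversion on the other rows (n = 7, two-sided, as printed).** Implied r is 0.62 for total AHI, 0.89 for supine AHI, 0.87 for maximal inspiratory pressure, 0.46 for maximal expiratory pressure and 0.92 for tongue strength. All are attainable, so the method does not flag every row.

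**The case against.** The core arithmetic is not in dispute. The fair counter-arguments concern how far it reaches.

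- **Other tests.** The document says that the analysis includes paired t-tests, which does not exclude others. With SDs about as large as the means for a rate that cannot be negative, skew is likely, and a log-scale or rank test would be a natural choice. The limit on SD_diff does not bind a test on transformed values. A signed-rank test by normal approximation, without continuity correction and with a rank sum of 3, gives z = (14 − 3)/√35 = 1.86 and p = 0.063, close to 0.064 but not equal to it. This stands: only the variants tried are ruled out as ordinary explanations. If another test was used, though, the row should say so.
- **The benchmark from the other rows is loose.** Several are printed to whole numbers. At their own rounding limits, expiratory pressure spans r of about 0.29 to 0.62, and tongue strength about 0.80 up to 1. Correlations for pressure and strength also say little about a respiratory event index. This stands, so any p drawn from that range is only illustrative. The requirement of r ≥ 0.9987 does not depend on it.
- **The p-value may be right.** If a mean or an SD is the misprint, 0.064 could be correct and the evidence would not be misstated. This stands: the document cannot identify the faulty figure.
- **Small consequence.** No row crosses 0.05, and this outcome is not identified as primary. This is true, and it limits the priority of the point without resolving the inconsistency.

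**Conclusion.** The concern holds. Read as a two-sided paired t-test on 7 raw-scale pairs with ± as SD, the printed row is internally impossible: its smallest attainable p is 0.108. Once rounding is allowed, 0.064 is possible but not credible, since it needs a correlation of at least 0.9987. Either the p-value, a mean or an SD is wrong, or the row uses an undisclosed n, participant set, sidedness or test.

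For scale, if the non-supine correlation lay in the range of the other rows as printed (0.46 to 0.92, a loose assumption), p would be 0.86 to 0.66. A p of 0.64 would also fit (SD_diff 2.69, r = 0.93), so a misplaced decimal is one possible explanation, but it is unconfirmed. The printed 0.064 may therefore overstate the evidence for a non-supine effect. Neither it nor the recalculated values for the figures as printed fall below 0.05, so nothing changes status at that conventional level. The row should be corrected; it does not undermine the other rows.

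**What to change.** Re-run the non-supine paired t-test from participant-level data, on exactly the pairs that produced the printed means and SDs, and correct whichever figure proves wrong. In that row, report the number of pairs and the mean paired change with its 95% CI, and label the ± values. If a different n, participant set, sidedness, transformation or test was used, say so beside the row.

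The cost is one re-run of an existing test and a one-line correction. The only downside is that the p-value may become less favourable; if 0.064 is right, the same check will confirm it.
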